2. HYPOTHESIS AND OBJECTIVES

Specific aim 1: To assess the effectiveness of MPI, versus standard care, in improving adherence to IVT follow-up appointments at 6, 12 and 18 months (main timepoint for primary outcome) *in patients with nAMD and DME requiring long term management* (primary outcome).

Hypothesis 1: *Compared to those in standard care, patients in the MPI group will have higher adherence to long-term follow-up appointments and IVT therapy.*

Specific aim 2A: Assess the effectiveness of MPI, versus standard care, in improving domain-specific CAT scores at the various follow-up timepoints (secondary outcome).

Hypothesis 2A: *Compared to those in standard care, patients in the MPI group will have greater gains in domain-specific CAT scores at each follow-up time point.*

Specific aim 2B: Assess the effectiveness of MPI versus standard care in improving visual acuity (VA), contrast sensitivity (CS), disease free intervals between IVT (as measured on optical coherence tomography (OCT) (secondary outcomes).

Hypothesis 2B: *Compared to those in standard care, patients in the MPI group will have greater VA and CS gains and achieve longer disease-free intervals between IVT at each follow-up time point.*

Specific Aim 3: To assess implementation outcomes of the MPI such as acceptability, adoptability, appropriateness, feasibility, fidelity.

Hypothesis 3: *Using a mixed methodology, with quantitative and qualitative outcome measures as reported by patients, caregivers, clinicians, nurses and allied health professionals, MPI will be an appropriate, adoptable, acceptable, feasible intervention with good fidelity.*

Specific Aim 4: To assess the cost-effectiveness of the MPI for improving adherence to IVT, considering its potential impact on long term visual acuity (VA) loss and QoL adjusted years (QALYs)

Hypothesis 4: *The MPI is incrementally cost-effective relative to standard care, based on accepted willingness-to-pay thresholds⁴².*

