|---------------------|---------------|---------------------|---------------|
| Item Bank | Interventions | Item Bank | Interventions |
| Visual symptoms | (2) | Activity Limitation | (2), (3) |
| Activity Limitation | (2), (3) | Lighting | (2) |
| Emotional | (1), (4) | Emotional | (1), (4) |
| Health Concerns | (1), (4) | Concerns | (1), (4) |
| Convenience | (1), (4) | AMD management | (1), (4) |
| Lighting | (2), | | |
| Social | (4) | | |
| Economic | (4) | | |

- In the standard care arm, the treating clinician will be masked from the CAT scores and will use his/her own discretion when recommending the treatment regimen or when making any appropriate nurse or allied health referrals, independent of the CAT scores. The CAT scores will be recorded by the clinical research coordinator at baseline and follow-up visits for comparison to the MPI arm.
- For those patients who do not have sub-optimal CAT scores at baseline, they will be assigned to an observational study group (Cohort 2) to continue to undergo routine clinical care and at the assigned study time points, they will be reassessed for any changes in their CAT scores and will undergo randomisation into the RCT if their scores have dropped below 50 or have reduced by 25% from the baseline visit. For those patients who do not experience sub-optimal CAT scores or a significant drop in their CAT scores during the duration of the study, they will still have their data collected at

all study visits based on the protocol but will not undergo randomisation. If any of these cohort patients show non-adherence to clinic visits during the duration of the study, they will be eligible for “rescue” MPI according to the clinician’s discretion at their next study visit and will be analysed as a separate sub-group.

Study schedule and outcome measures

The primary outcome is the comparison of adherence rates to IVT treatment between the MPI arm versus standard care (Cohort 1) at 6, 12 and 18 month time points (+/- 8 weeks) (main outcome) (Specific aim 1). The follow-up study visits will be coordinated with the planned clinical standard care visits, only if the patient does not have a routine clinical care visit scheduled within the range of the follow-up time-points will an additional study visit be scheduled.

Adherence is defined as

- 1) patient attends all follow-up appointments within 1 month of the planned follow up date, and
- 2) patient receives IVT within 1 month of when the doctor recommends IVT.

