At each follow up time point, based on the previous scheduled follow-up appointments and recommended IVT schedule, the study team will assess if the patient has been “adherent” or “non-adherent”. If the patient does not visit the clinic within the range of the follow-up time points or does not attend the scheduled study visit, phone calls will be made to determine reasons or barriers for adherence. A remote invitation to complete the CAT questionnaire will also be sent to these patients or if uncontactable, they will be approached and interviewed at their next clinical visit. For previously treated patients, previous adherence status up to 2 years prior to study enrolment for the time of IVT treatment will be recorded by the study team from medical records.

Secondary outcome measures will be assessed at baseline and 6, 12, and 18 month follow up visits (+/- 8 weeks) including:

- CAT scores (Specific aim 2A) from the CAT questionnaire database
- Visual function -Monocular and binocular presenting corrected VA and CS (Specific aim 2B) will be collected from the clinical records. If data are not present, the CRCs will conduct these tests on participants using standardized protocols.
- Disease free intervals as defined by the maximum IVT treatment interval where no disease activity recurrence is detected on OCT will be collected from clinical records and OCT images from the clinical database (Specific aim 2B)
- Tertiary outcome measures include the acceptability, adoptability, appropriateness, feasibility, fidelity through mixed method testing with interviews and questionnaires (Specific aim 3).
- The costs of MPI, baseline and 18-month assessment of Euro-quality of life (EQ-5D) to assess QALYs (Specific aim 4)

Qualitative and quantitative analysis of key stakeholders (Specific aim 3)

The PI, assisted by their Co-Is and collaborators, will identify eligible individuals for qualitative interviewing that will be performed with major stakeholders between 6 to 15 months timeline. These include the clinicians, nurses and the allied health specialists (OP, OT and SW) who will be involved in administering the MPI, and patients and care-givers who receive the MPI. Potential individuals will be contacted over email or phone call, and a trained study team will follow up on affirmative responses by obtaining written informed consent to carry out the following study procedures:

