8. SAMPLE SIZE AND STATISTICAL METHODS

8.1. Determination of Sample Size

Specific Aim 1 and 2: The primary outcome comparison of adherence rates to IVT treatment between the MPI arm versus standard care at various follow-up time points with 18 months as the main time point. It is estimated that the baseline non-adherence rate with standard care arm is 40% (SD=2). Considering a reduction of the non-adherence rate to 20% as a clinically significant difference, and assuming a power of 80% and a two-sided level of significance at 5%, the minimum sample size

required is 79 patients per arm (rounded up to 160 patients in total). Assuming a maximum 20% dropout in the study we estimate a sample size of 200 patients (Specific aim 1).

For secondary outcomes such as the improvement of QoL as assessed by the various CAT domain scores, we assume a modest effect size difference of 0.5 between the two arms. Using a power of 80%, a two-sided level of significance at 5%, and the maximum 20% dropout rate, we estimate the required sample size is 158 (79 per arm) (Specific aim 2A). Hence, this is included in the larger sample size calculated above.

Specific aim 3: There is no *a priori* sample size required for qualitative interviews. We will continue our semi-structured interviews until thematic saturation is reached (i.e. no new themes emerge). Based on previous studies by our group^{31,67}, we anticipate the need to interview between 5-10 participants for each stakeholder group to obtain data saturation, broadly: (a) clinicians using CATs and MPI, (b) NE, OP, OT and SW involved in administering MPI (c) patients involved in this study, and (d) caregivers of patients. For the purposes of estimating a budget for this grant proposal, we state an indicative sample size of 40 interview participants i.e. 10 in total for stakeholder group a and b, and 30 for stakeholder group c and d (patients and caregivers).

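### Study calls about barriers after a missed study visit are not held until the 1-month grace ends, so they may act on the adherence endpoint in the standard care arm

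*Protocol*

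**What the plan says.** Specific aim 1 (Protocol section 2) is: "To assess the effectiveness of MPI, versus standard care, in improving adherence to IVT follow-up appointments". Under the study schedule in section 5, the first part of the adherence definition is that the "patient attends all follow-up appointments within 1 month of the planned follow up date". The second part requires the injection within 1 month of its being recommended. One breach makes the patient non-adherent.

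On where study visits fall, section 5 says: "The follow-up study visits will be coordinated with the planned clinical standard care visits". A separate study visit is added only if no routine visit lies within 8 weeks either side of the 6, 12 or 18 month time point.

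The same section gives two triggers for a phone call, joined by *or*. The first is no clinic visit within that window. The second is that the patient "does not attend the scheduled study visit, phone calls will be made to determine reasons or barriers for adherence". These patients also get a remote invitation to complete the CAT questionnaire, and those who cannot be reached are interviewed at their next clinical visit. No call timing, script or restriction to one arm is given.

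Section 8.1 assumes 40% non-adherence under standard care and continues: "Considering a reduction of the non-adherence rate to 20% as a clinically significant difference". It makes no mention of the calls.

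**The concern.** The call is a trial procedure, not part of the comparator that the objective names. It asks a patient who has just missed a visit what is keeping them away. That overlaps with what the MPI does, which is to find and address barriers to adherence. Because study visits usually are clinic appointments, the missed visit is usually one that counts for the endpoint, and for a month it can still be kept on time. A standard care patient who would have become non-adherent could be prompted back within that month and be counted as adherent.

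If calls recover a similar share of misses in each arm, the control arm has more to recover and the absolute difference shrinks. The trial would then estimate MPI against standard care plus study contact. A null result would be harder to read, because the calls might have done part of the MPI's work in both arms.

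**Working it through.** **The plan's own figure.** Inputs from section 8.1: 40% v 20% non-adherence, 80% power, two-sided 5%. The unpooled normal formula gives (1.960 + 0.842)² × (0.4×0.6 + 0.2×0.8) / 0.2² = 78.5, so 79 per arm, as stated. Then 160 / (1 − 0.20) = 200, also as stated. Exact enumeration of the Pearson chi-square test gives power of 79.5% at 79 per arm and 80.1% at 80 per arm.

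**When a call can fall inside the grace month.** The second trigger has no stated delay. The first waits for the 8-week window to close. An appointment planned *d* weeks after the time point sees the window close 8 − *d* weeks after its planned date. For *d* = 0 that is 8 weeks, after the grace has ended. For *d* above about 4 it is under a month, so even the first trigger can act while the appointment can still be kept on time.

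**Possible effect on power.** The documents give neither the number of appointments nor the effect of a call, so these are assumptions: K appointments in 18 months, 3 of them study visits, and a share *r* of missed study visits recovered within the month by the call.

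*Independent misses.* The per-appointment miss rate *p* solves 1 − (1 − p)^K = 0.40 or 0.20. For K = 9, p = 5.52% (control) and 2.45% (MPI). Non-adherence with calls is 1 − (1 − p)^(K−3) × (1 − p(1 − r))³.

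For K = 9 and r = 0.5:
- Control: 1 − 0.9448⁶ × 0.9724³ = 34.6%.
- MPI: the same formula gives 16.9%.

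| K | r | Control v MPI | Exact power, 80 per arm |
|---|---|---|---|
| – | 0 | 40% v 20% | 80.1% |
| 9 | 0.10 | 38.9% v 19.4% | 78.9% |
| 9 | 0.25 | 37.3% v 18.5% | 77.1% |
| 9 | 0.50 | 34.6% v 16.9% | 73.8% |
| 9 | 0.75 | 31.8% v 15.4% | 69.8% |
| 6 | 0.50 | 31.6% v 15.4% | 69.4% |
| 12 | 0.50 | 36.0% v 17.7% | 75.6% |

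*Clustered misses.* Let the miss probability vary between patients (beta-binomial), with the mean again set to give 40% and 20%. A recovered study visit is then less often the patient's only breach. For K = 9, power at r = 0.25 and r = 0.50 is:
- ICC 0.2: 78.4% and 76.6%.
- ICC 0.3: 78.8% and 77.3%.
- ICC 0.5: 79.2% and 78.2%.

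**A check with a different model.** If calls convert 10% of non-adherent patients in each arm (36% v 18%), normal-approximation power falls from 79.4% to 73%. If both arms instead drop 5 points (35% v 15%), it rises to 84%. That requires recovering 5/20 = 25% of non-adherent MPI patients against 5/40 = 12.5% of controls.

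**The case against.** Several points against the concern stand, and they limit it.

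- **Timing.** A reader might infer that the call goes out at once. The protocol does not say so; it is silent. The preceding sentence in section 5 has the team judge adherence at each time point, so asking for reasons afterwards is a natural reading. Nothing, however, holds the call until then.
- **Which visits.** The second trigger could be meant only for the added study visits, which may not count as planned clinical appointments. The text does not limit it that way, and the first trigger can still fall inside the grace month for appointments planned late in the window.
- **Nature of the call.** A reader might infer a recall service. The call is described only as finding reasons; nothing says that it reminds, rebooks or counsels. A prompting effect is plausible but not stated.
- **Bias between arms.** A reader might infer that unmasked callers press harder in one arm. Section 5 does not say who makes the calls or whether they are masked. The procedure is common to both arms, so the randomised contrast holds. A fall in the control arm alone has no basis in the text.
- **The 40%.** Section 8.1 gives no source, so it cannot be checked what contact that figure already includes.
- **The size.** A 50% recovery from a reasons-only call has no support in the documents. Independence is the less favourable assumption for power. The model leaves out the injection criterion, which a recovered visit need not satisfy.
- **Other contact.** CAT links before appointments, the CAT invitation to non-attenders and the per-visit reimbursement all remain. Changing the call does not make the comparator pure, but it removes the contact aimed most directly at a missed appointment.

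**Conclusion.** The point holds in a limited form. As written, a study procedure can reach standard care patients while the primary endpoint is still open to change, and the sample size makes no mention of it. The consequence is possible dilution and a comparator that may not be plain standard care.

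A reader might go further and conclude that the 80% power no longer holds. The documents do not support that. Under the assumptions above (9 appointments, 3 of them study visits), the loss is about 1 point at 10% recovery, 3 at 25% and 6 at 50% with independent misses. With clustering at ICC 0.2 to 0.5 it is about 2 to 3.5 points at 50% recovery. Fewer appointments make it larger. If calls have no effect there is no loss, and an equal absolute fall in both arms would raise power. The 80 per arm is also what remains after the full 20% dropout; 100 per arm would give 87.6% at 40% v 20% (normal approximation).

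This is a cheap improvement to the design rather than an error in the plan's figures.

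**What to change.** In Protocol section 5, state that the study team's call about barriers is made only after the 1-month grace for that appointment or recommended injection has ended and its adherence status has been recorded from clinic records. Use the same reasons-only script in both arms. Log the date of every study call, so that attendance following a call can be identified in a sensitivity analysis. Leave the clinic's usual handling of missed appointments unchanged.

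The cost is a short addition to section 5 and one date field on the case report form. Reasons for non-attendance are collected a few weeks later, with slightly poorer recall. No extra staff, visits or patients are needed.

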The proposed MPI consists of a medical consultation to optimise patients' treatment regimen, address concerns about their disease and treatment, explain advantages and disadvantages about the type of IVT medication and potential of increased treatment intervals between IVT, and address other patient and care-giver concerns.

Importantly, CAT scores will be available to the clinician to guide the consultation. Based on sub-optimal CAT scores, referral to one or a combination of services will be initiated by the study team according to a preset protocol (**Table 2**):

- (1) a referral to NE, which would include a session with a trained IVT nurse educator, who would use previously validated hard copy and digital education resources to educate the patients on their disease, symptoms, progression, and need for treatment. Factors which may cause anxiety for IVT patients such as side effects and adverse events will be addressed and the need for IVT adherence to maintain long-term vision will be reinforced. The patients would be reminded about the availability of the IVT hotline to address concerns and appointment issues.

- (2) a referral to OP who, after a needs assessment, would then carry out a comprehensive low vision assessment that includes refraction, CS, reading acuity, determination of reading goals and prescribing of suitable optical aids. OPs will assess and address any vision-related issues that may hinder reading specific tasks, navigation and other ADLs, which may be barriers to IVT adherence. They can further discuss the patient's expectations about their visual recovery and the need for IVT to maintain vision.
- (3) a referral to OT who, after a needs assessment, would provide advice about optimal lighting and, contrast perform activities of daily living retraining and functional/community mobility training, provide patient/family education and, if required, home modification to facilitate independence in ADLs, which may may allow better access to IVT appointments promoting adherence.
- (4) a referral to medical SW who, after a needs assessment, would provide the necessary emotional counselling, financial counselling and referral to community care services and other relevant support services addressing relevant barriers related to adherence to IVT.

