- Following baseline assessment, **participants with suboptimal CAT scores (Cohort 1-<50 in any domain)** will be included in the RCT and randomly allocated in a 1:1 ratio to either the intervention group (personalised multi-disciplinary protocolised intervention, MPI) or the control group (standard care). Randomisation will be conducted using a computer-generated random sequence created by an independent biostatistician not involved in recruitment or outcome assessment. To ensure balance across disease types, randomisation will be stratified by diagnosis (neovascular age-related macular degeneration [nAMD] vs. diabetic macular edema [DME]). Allocation concealment will be maintained using sequentially numbered, opaque, sealed envelopes prepared by an independent study coordinator. The envelopes will only be opened after baseline data collection to assign participants to their respective groups. Co-Is that are not treating clinicians and data analysts will remain blinded to group allocation, although masking of participants and principal investigator and Co-Is who are the treating clinicians will not be feasible due to the nature of the intervention.

- For the MPI arm, the CAT scores integrated into the electronic medical records will be used to formulate **an automated protocolized standardized MPI for all patients based on the domain specific scores that are sub-optimal** (See **Table 2**). All MPI patients will receive *a medical consultation (compulsory) and an addition of Intervention 1-4 (electives, 1) NE, 2) OP, 3) OT, 4) SW*. In the MPI arm, these referrals would be automatically triggered by the study team based on baseline CAT scores and the treating clinician will be informed. The MPI visits will take place on the same day as standard clinical visits where possible, however additional MPI study visits may be needed if there are scheduling challenges. Referral adherence to the MPI appointments and intervention will be assessed.

Sub-optimal scores are defined as any domain where the scores are below 50 at baseline or have reduced by 25% from the baseline visit. Table 2 summarizes the MPI interventions that are relevant to each CAT domain. A tailored MPI will be formulated and recommended to the patient at baseline, or at a follow-up time-points where domain scores decrease, and the MPI should be completed within 4 months.

Table 2: Standardised personalised MPI based on sub-optimal CAT domain-specific scores

| Ret CAT | | MacCAT | |

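### Follow-up contrast sensitivity can come from a different tester and method by arm, because the clinical record is used first and only the MPI arm has protocol-triggered optometrist testing

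*Protocol*

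**What the plan says.** Protocol section 5 (Study schedule and outcome measures) sets an order of sources for the two visual-function outcomes of Specific aim 2B. First, "Monocular and binocular presenting corrected VA and CS (Specific aim 2B) will be collected from the clinical records". Then, "If data are not present, the CRCs will conduct these tests on participants using standardized protocols". So the standardised test is the fallback. No chart or examiner is fixed for the record values, and nothing says whether a reading made during an MPI session counts as a record value.

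Section 1 describes the optometrist part of the MPI as a "comprehensive low vision assessment that includes refraction, CS, reading acuity, determination of reading goals and prescribing of suitable optical aids". Under section 5, in the MPI arm "these referrals would be automatically triggered by the study team based on baseline CAT scores". Table 2 attaches the optometrist to three of the eight RetCAT domains (visual symptoms, activity limitation, lighting) and two of the five MacCAT domains (activity limitation, lighting). In standard care the clinician "will use his/her own discretion when recommending the treatment regimen or when making any appropriate nurse or allied health referrals".

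On timing, section 5 places the follow-up outcomes at 6, 12 and 18 months with a window of 8 weeks either side. An MPI may be set at baseline or at a later time point if scores fall, and has 4 months for completion. MPI sessions share the day of the standard visit where that can be arranged. On masking, "Co-Is that are not treating clinicians and data analysts will remain blinded to group allocation"; coordinators and optometrists are not on that list.

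**The concern.** The source of a CS value depends on whether the record already holds one, and the intervention can change that in one arm. An MPI patient with an optometrist reading in the record would contribute that reading. A comparable control patient with no CS on file would contribute the coordinator's reading, by another procedure. A between-arm difference in follow-up CS could then partly reflect who tested and how. Hypothesis 2B predicts greater VA and CS gains with the MPI, so a shift from the change of source could be read as support for it, or could hide a true gain. Analysis cannot repair this later, because a standardised CS test that was not done cannot be recovered.

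**Working it through.** The plan states no figure on this point, so the check is to set the rules side by side and then work out the timing.

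**1. Does the rule treat the arms alike?**

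| Step | MPI arm | Standard care |
|---|---|---|
| First source of CS and VA | Clinical record | Clinical record |
| Optometrist session with CS and refraction | Triggered by domain score | Clinician's discretion |
| Coordinator's standardised test | Only if the record is empty | Only if the record is empty |

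The rule is the same on paper, but its first step draws on a record that the intervention can fill in one arm.

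**2. Baseline.** Section 5 has the allocation envelope opened after baseline data are collected, so baseline source cannot depend on arm. It follows that change from baseline does not cancel a difference in source at follow-up.

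**3. Can an optometrist reading fall in an outcome window?** One month is 365.25 / 12 / 7 = 4.348 weeks, so 8 weeks is 8 / 4.348 = 1.84 months.

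- Month 6: 6 ± 1.84 gives 4.16 to 7.84.
- Month 12: 12 ± 1.84 gives 10.16 to 13.84.
- Month 18: 18 ± 1.84 gives 16.16 to 19.84.

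An MPI set at baseline and finished on time ends by month 4.00, just before the first window opens at 4.16. It enters the window only if delayed. An MPI set at a month-6 visit may run to 6 + 4 = 10.00, and the part from 6 to 7.84 (1.84 of the 4 months) lies in the same window; the rest ends before the next window opens at 10.16. The pattern is the same at months 12 and 18. A third route is a session on the study-visit day itself, which section 5 favours for MPI sessions in general.

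**4. CS or VA?** Section 4.2 describes VA testing as part of clinical care and does not name CS. Study visits are coordinated with routine visits. A clinic VA should therefore be on file in both arms, whereas a CS value may often be on file only because an optometrist took it. Section 1 lists CS explicitly for the optometrist session. It lists refraction and reading acuity but not distance VA, so a post-refraction VA reading is possible rather than stated.

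**5. Size.** The documents do not give the share of patients with an in-window optometrist reading, or the difference between the two test methods. As an illustration only, assume 80 evaluable patients per arm (section 8.1: 160 in total before dropout), no true effect, two-sided 5%, an excess share f of MPI patients whose reading comes from the optometrist, and a shift of b standard deviations in those readings. The standardised difference is f × b, its z-value is f × b / √(2/80) = f × b / 0.158, and the false-positive rate is Φ(z − 1.96) + Φ(−z − 1.96).

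| f | b | f × b | False-positive rate |
|---|---|---|---|
| 0.25 | 0.2 | 0.05 | 6.2% |
| 0.25 | 0.5 | 0.125 | 12.4% |
| 0.50 | 0.3 | 0.15 | 15.8% |
| 0.75 | 0.5 | 0.375 | 66% |

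Step 3 limits the routes into a window, so the lower values of f are the more relevant ones. Both f and b are assumptions.

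**The case against.** The strongest reply is that the problem will be uncommon. VA is tested routinely in both arms. A baseline-triggered MPI should be over before the first window opens. The optometrist session is elective and depends on domain scores, and controls may also be referred. When a referral is set at a follow-up visit, VA should already be on file and the coordinator would test a missing CS at that visit in either arm, so a later optometrist reading would not be needed. All of this stands and narrows the point. It does not close it: same-day and delayed sessions remain, and no rule says which value is used when an optometrist reading is in the record.

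A second reply is that coordinators are not listed as masked, so moving CS testing to them has its own risk. That is fair and belongs with the fix.

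Three stronger readings are tempting, and the protocol does not support them.

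- **That a gain in presenting VA from a new correction is bias.** Refraction and optical aids are part of the randomised package, and Hypothesis 2B compares VA and CS gains between arms without saying that they must come through adherence. Such a gain is a real effect of the MPI and should be described as one.
- **That a specific number of letters is gained artificially.** No input for such a figure is in the protocol, and it would mix the real effect of new correction with differences between testers.
- **That the cost-effectiveness result is undermined.** Section 8.2 extrapolates long-term VA from published trajectories by adherence status. It does not say that the aim 2B difference drives that extrapolation.

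**Conclusion.** The concern holds in limited form. As written, the source rule allows follow-up CS to be obtained by a different tester and method in the MPI arm than in standard care, and nothing else in the protocol prevents it. This can happen when an optometrist session falls on the study-visit day, is delayed past month 4, or is triggered at a follow-up visit and held within the next 1.84 months. The risk is mainly to CS, smaller for VA, and absent at baseline. The primary adherence outcome is not affected. The size cannot be derived from the documents; it depends on how often an in-window optometrist reading is used and on how far the two methods differ. This is a worthwhile and inexpensive correction to a secondary outcome, not a threat to the trial's main conclusion.

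**What to change.** In section 5 (Study schedule and outcome measures), replace the record-first rule for Cohort 1 with one source per outcome at baseline and at months 6, 12 and 18:

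- **CS:** the coordinator's standardised test, in both arms.
- **VA:** the routine clinic test, in both arms, with the patient's presenting correction; the coordinator's test if that value is missing.
- **Both:** readings taken in MPI service sessions are never used as outcome data.

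When aim 2B is reported, state that presenting VA includes any effect of new correction supplied through the MPI.

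The cost is a few more minutes of coordinator testing at visits where a record value would otherwise have served. The coordinators already have the standardised protocols for these tests. Because they are not listed as masked, the section should also require the same test script to be followed identically in both arms; an assessor masked to allocation would be better where one is available. The change should be made before follow-up readings accrue.
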